STUDY PROTOCOL PLAN AND STADISTICAL ANALYSIS PLAN (SAP)

UNIVERSITY CEU CARDENAL HERRERA

Principal investigator: [name] [name]

TITLE: Second-generation Radiofrequency Application and Specific Therapeutic Exercise as a Treatment for Stress Urinary Incontinence Due to Urethral Instability. Randomised Clinical Trial

Research and Ethics Committee of CARDENAL HERRERA CEU UNIVERSITY:
CEEI25/646

NCT ID:

DATE: 01-14-2026

STUDY PROTOCOL PLAN

Objectives:

The objectives of our study have been the following:

The purpose of this study is to evaluate the correlation between urethral instability, assessed by ultrasound analysis of the bladder neck opening, and the severity of SUI, assessed by validated standard questionnaires. The determination of standard ultrasound parameters that allow urethral instability to be related to the severity of SUI would be a valuable finding for accurately diagnosing the severity of SUI using low-cost, easy-to-use imaging methods.

A randomized, single-blind clinical trial will be conducted in women with stress urinary incontinence (SUI). Participants will be randomly assigned to one of three intervention groups: radiofrequency (RF), specific pelvic floor muscle exercise (PFMT), or combined treatment (RF + PFMT). The study will be carried out at Clínica Traña (San José, Costa Rica), with an expected start date in 2025. The study will adhere to the principles of the Declaration of Helsinki and current European data protection regulations.

Adult women with urinary leakage and a bladder neck opening greater than 90°, assessed by functional ultrasound, will be included. Women with other pelvic floor disorders, pregnancy, recent treatments (RF, PFME, hormonal or laser therapies), relevant neurological, metabolic, or cardiovascular conditions, prior pelvic surgery, active infections, or contraindications to the interventions will be excluded. The estimated sample size is 117 participants (39 per group), calculated to detect statistically significant differences with 80% power and a 5% significance level, allowing for a 30% dropout rate.

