Before the intervention, all participants will undergo physical examination, digital palpation, and functional pelvic floor ultrasound, as well as complete validated questionnaires assessing urinary incontinence severity and quality of life (ICIQ-SF, King's Health Questionnaire, and Sandvik Severity Index). These assessments will be repeated at the end of the intervention and at 15 days, 3 months, 6 months, and 12 months post-intervention.

Randomization will be performed using statistical software, and outcome assessors will remain blinded to group allocation. Data will be coded and securely stored, ensuring participant confidentiality in accordance with the General Data Protection Regulation (EU 2016/679).

The RF intervention will consist of five weekly sessions of non-ablative fractional vaginal radiofrequency with temperature control and standardized parameters. The PFME program will comprise a structured core and pelvic floor exercise protocol supervised by physiotherapists, conducted twice weekly over a 16-week period. The combined group will receive both interventions.

Primary outcomes will include pelvic floor muscle strength and function (Oxford scale, endurance, and fatigability), ultrasound parameters (bladder neck opening, urethral hypermobility, and presence of prolapse), and validated questionnaires assessing urinary incontinence severity and quality of life.

Statistical Analysis Plan (SAP)

Data will be expressed as mean \pm standard deviation or as a percentage. The distribution of the sample will be determined using the Kolmogorov-Smirnov test. For quantitative variables, depending on the type of variable, Student's t-test or Mann-Whitney U test will be performed. The correlation between variables will be analyzed using Spearman's correlation. In the case of qualitative variables, the association between variables will be analyzed using bivariate or multivariate logistic regression, as appropriate, and contingency tables. The statistical significance of the difference between them will be evaluated using Pearson's χ^2 test. Statistical significance will be assumed with p-values <0.05 .

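### The plan allows for 30% dropout but states no analysis set or missing-data method, so its named tests would compare only the women with a value and could be biased if loss depends on outcome and differs by arm

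*Combined protocol and SAP*

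**What the plan says.** The Study Protocol Plan states: "The estimated sample size is 117 participants (39 per group"), with "80% power and a 5% significance level" and "allowing for a 30% dropout rate". The dropout figure appears there only, as an inflation of the sample size. The text does not say by which visit the loss is expected; I take it as cumulative to the last one.

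Outcomes are assessed at baseline, at the end of the intervention, and 15 days, 3, 6 and 12 months later, so there are five post-baseline visits. Radiofrequency is "five weekly sessions of non-ablative fractional vaginal radiofrequency". The exercise programme is "conducted twice weekly over a 16-week period". The combined arm receives both.

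The first paragraph of the Statistical Analysis Plan names the tests: "For quantitative variables, depending on the type of variable, Student's t-test or Mann-Whitney U test will be performed". It adds Spearman correlation, logistic regression, contingency tables and Pearson's chi-square, and sets the threshold: "Statistical significance will be assumed with p-values <0.05". The rest of the SAP covers the diagnostic performance of bladder neck opening. No section defines an analysis population, a treatment of absent values, a model that uses several visits together, or a sensitivity analysis.

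**The concern.** A t-test, a Mann-Whitney test, a chi-square test or a logistic regression at a given visit leaves out any woman without a value at that visit. If she gave a baseline and three follow-up assessments and then left, none of that enters the 12-month comparison. Inflating the sample from about 27 to 39 per arm protects the number of women analysed, and so the power. It does not protect the randomised comparison against selective loss.

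The attendance burden is unequal by design. If women who are still leaking leave more readily, and one arm loses more women or loses them for different reasons, the women left in the arms are no longer comparable. The 6- and 12-month results are the most exposed, for quantitative and categorical outcomes alike. An apparent arm difference could then pass the 5% threshold without a treatment difference.

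**Working it through.** **Figures in the plan.** 39 × 3 = 117. Women left per arm at the allowed dropout: 39 × 0.70 = 27.3, or 81.9 of 117 overall. In reverse, 27 / 0.70 = 38.6, rounded up to 39, so the stated size fits a target of 27 per arm. It also fits 30 × 1.3 = 39. The target itself cannot be reproduced, because no effect size, SD or response rate is given; the text says only "calculated to detect statistically significant differences". Scheduled sessions: 5 for radiofrequency, 2 × 16 = 32 for exercise, 5 + 32 = 37 for the combined arm.

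**When bias arises, by hand.** Assume true success of 50% in both arms. Observed success = retained successes / all retained. All dropout patterns here are assumptions.

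- Random loss, equal or unequal: 50% against 50%, difference 0.
- 30% lost in both arms, failures three times as likely to leave in both (45% against 15%): 0.5 × 0.85 / 0.70 = 60.7% in each arm, difference 0.
- Same 3:1 pattern, 40% lost in one arm (60% of failures, 20% of successes) and 20% in the other (30%, 10%): 0.40 / 0.60 = 66.7% against 0.45 / 0.80 = 56.3%, difference 10.4 points.
- 30% lost in both arms, 3:1 in one and random in the other: 60.7% against 50%, difference 10.7 points, with a false-positive rate of about 12% by normal approximation.

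So bias needs two things together: loss related to outcome, and a difference between arms in rate or mechanism.

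**Size on a continuous outcome.** Simulation with 39 per arm, five post-baseline visits, between-visit correlation 0.6 and no true difference. The odds of leaving double or triple per SD worse at the last visit seen. A t-test is run on 12-month completers. None of these settings except the 39 and the visit count comes from the documents. Ranges cover several independent runs of about 1,500 to 2,000 trials per scenario.

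| Dropout, RF vs an exercise arm | Completer difference | t-test p<0.05 |
|---|---|---|
| 30% vs 30% | about 0 | 4.3 to 5.8% |
| 25% vs 35% (odds ratio 2 only) | 0.05 SD | 5.5% |
| 15% vs 37.5% | 0.09 to 0.15 SD | 5.4 to 9.0% |
| 15% vs 45% | 0.14 to 0.20 SD | 7.5 to 11.8% |

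The third row averages 30% over the trial: (15 + 37.5 + 37.5) / 3. The fourth averages 30% over the two arms compared: (15 + 45) / 2. Simulation error near 5% is about 0.5 points (√(0.05 × 0.95 / 2000) = 0.0049), so the lowest results in the third row cannot be told apart from 5%.

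In the main scenarios, multiple imputation by arm from the earlier visits left a bias of 0.02 SD or less, with 2.9 to 4.8% rejections. That is a favourable test, because loss depended only on observed values. When loss was made to depend on the unseen current value (15% vs 37.5%), imputation left 0.04 to 0.08 SD, against 0.13 to 0.18 SD for completers.

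**Cost of a heavy imputation model.** At 27 per arm, 80% power corresponds to a difference of (1.96 + 0.84) × √(2/27) = 0.76 SD, used here as an assumed effect. With equal 30% dropout, completers had about 78 to 81% power. By-arm imputation with three uninformative covariates added to the visits had 68% with 5 imputations and about 72% with 30.

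**The case against.** A reader might infer that the late comparisons will favour whichever arm loses more of its failures, or that exercise will be flattered over radiofrequency. The documents do not support this. They forecast no dropout by arm and say nothing on why women might leave. Session counts show unequal burden; they do not show that women still leaking leave more. Loss caused by burden alone and unrelated to outcome gives no bias, loss of improved women would reverse the direction, and supervised contact might improve retention.

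A reader might also infer that the SAP prescribes a completer analysis. It does not; it is silent. The named tests are compatible with imputation, and the defect is the absent paragraph. Nor does the SAP say which visits or which pairs of arms are tested, so a late arm comparison is inferred from the visit schedule and the outcome list. Nothing shows that the bladder-neck diagnostic analysis depends on 12-month data, so the point is confined to the randomised outcomes.

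Finally, the effect is modest. A 25% against 35% split is close to harmless under the milder mechanism. Error rates well above the table can be produced by letting only failures leave an arm, but nothing in the plan points to so extreme a pattern.

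All of this stands, and it makes the bias conditional and limits its size. It does not supply the missing rule: nothing beyond the named tests tells an analyst what to do with the women lost.

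**Conclusion.** The omission is established from the text: a 30% dropout allowance, five post-baseline visits, tests that use only observed values, and no analysis set or missing-data method. Followed as written, a late comparison uses about 27 of 39 women per arm and discards the earlier visits of the rest.

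The bias is a conditional risk. With assumed dropout of 15% against 37.5 to 45% that depends on the last observed outcome, it is about 0.1 to 0.2 SD with roughly 6 to 12% false positives in place of 5%. It vanishes if loss is random, or equal and of the same kind in both arms. Because the plan gives no effect size, this bias cannot be set against a planned difference. The point should be corrected; confidence in its practical size is moderate, since every dropout mechanism used here is an assumption.

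**What to change.** Add one paragraph to the SAP, before outcome data are examined:

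- All randomised women are analysed in their allocated arm.
- Quantitative primary outcomes are compared with a likelihood-based repeated-measures model containing baseline, arm, visit and arm-by-visit, using every observed visit. The alternative is multiple imputation with a small predictor set (baseline and earlier visits) and at least 20 to 30 imputations, with the planned comparison run in each set and combined.
- Categorical outcomes are handled by the same principle.
- Dropout is reported by arm and visit.
- One delta-adjusted sensitivity analysis assumes that lost women did worse than predicted, by a stated amount.
- The observed-only tests are shown as supportive.

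This needs some analysis time. It requires no new data and no change to treatment, visits or sample size. The price is that the main result relies on missing-at-random, which reduces but does not remove bias when loss depends on values nobody saw; the sensitivity analysis is there to probe that. If imputation is chosen, the predictor list should stay short, because many predictors fitted to about 27 completers per arm cost power. The repeated-measures model was not simulated here; it is offered because it uses the same earlier visits under the same assumption.

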To evaluate the diagnostic capacity of bladder neck opening measured by ultrasound analysis in the classification of the severity of stress urinary incontinence, a logistic regression analysis was performed. The dichotomized severity of the Sandvick test (mild/moderate versus severe/very severe) will be taken as the gold standard. Demographic and clinical variables will be evaluated as possible covariates and included in subsequent models if they had a p-value < 0.200 .

Sensitivity, specificity, Youden's index (sensitivity + specificity - 1), and positive and negative likelihood ratios (LR+ and LR-) will be calculated for bladder neck opening at rest, during the Valsalva maneuver, the variation between the two, and for the maximum model with the three variables.

The optimal cutoff point for bladder neck opening at rest will be determined using the Youden index. Subsequently, this value will be transformed into clinical units (mm) by algebraic solving of the logistic model equation, adjusted for relevant covariates (age and BMI). This approach preserves the statistical fit of the model while providing a clinically interpretable threshold.

Studentized residuals, leverage values, and Cook's distances will be estimated to identify possible outliers and influential values in the dependent variable, the predictors, and the model as a whole.

Receiver operating characteristic (ROC) curves will be constructed to determine the area under the curve (AUC). Likewise, the Hosmer-Lemeshow goodness-of-fit test will be applied to compare the observed and expected frequencies of the model (considering $p > 0.05$ as an adequate fit). The accuracy of the probabilistic predictions will be evaluated using the Brier Score (lower values indicate better performance). The

analysis will be performed using SPSS Statistics 29.0 (IBM Corp.)

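### For quantitative outcomes the SAP names only t or Mann-Whitney tests and specifies no three-arm, baseline-adjusted or repeated-measures comparison of the randomised arms

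*Combined protocol and SAP*

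**What the plan says.** The Study Protocol Plan states that "Participants will be randomly assigned to one of three intervention groups": radiofrequency, pelvic floor exercise, or both. The sample size is given as "117 participants (39 per group), calculated to detect statistically significant differences with 80% power" at a 5% significance level, "allowing for a 30% dropout rate". Examination, palpation, ultrasound and questionnaires are done before treatment and then "repeated at the end of the intervention and at 15 days, 3 months, 6 months, and 12 months post-intervention". That is one baseline and five post-treatment measurements. Several families of outcome are called primary: muscle strength and function, ultrasound parameters, and questionnaires.

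In the first paragraph of the Statistical Analysis Plan, the comparison named for quantitative variables is that Student's "t-test or Mann-Whitney U test will be performed". Spearman's correlation is named for association. Regression, contingency tables and Pearson's chi-squared come under a different type of variable: "In the case of qualitative variables, the association between variables will be analyzed using bivariate or multivariate logistic regression". The rest of the SAP addresses another question, opening with "To evaluate the diagnostic capacity of bladder neck opening measured by ultrasound analysis". Its covariates, age and BMI among them, belong to that diagnostic model. No sentence of the SAP mentions treatment arm.

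**The concern.** A t or Mann-Whitney test compares two sets of values. With three arms and five post-treatment visits there are 3 x 5 = 15 possible pairwise tests for each quantitative outcome, before choosing between raw values and change from baseline. The SAP does not choose among them, so the choice could be made after results are seen.

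If the named tests are applied to the arms visit by visit, three things follow:

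- **Precision.** The baseline value is ignored, so estimates are less precise than the same data allow.
- **Missing data.** Each visit is analysed on the women still present. With 30% dropout foreseen, later comparisons can be biased if leaving depends on earlier scores.
- **Error rate.** Each test is judged at 0.05 with no rule for the three pairs of arms.

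**Working it through.** **What can be reproduced.** The planned 117 cannot be rebuilt, because no effect size, SD, reference outcome or test is given. Only the dropout step can be checked. 39 x 0.7 = 27.3, so about 27 evaluable women per arm; alternatively 39 / 1.30 = 30. Either fits.

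**Implied effect.** For a two-sample t-test, two-sided 0.05 (sidedness is assumed) and 80% power, the standardised difference is d = 0.777 with 27 per arm and d = 0.736 with 30.

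**Baseline adjustment.** With baseline-outcome correlation r, the residual SD shrinks by sqrt(1 - r²). The effective difference is then d / sqrt(1 - r²), and the equivalent unadjusted sample is 27 / (1 - r²).

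| r (assumed) | 0.777 / sqrt(1 - r²) | Power | Equivalent n per arm |
|---|---|---|---|
| 0 (t-test) | 0.777 | 80% | 27 |
| 0.3 | 0.777 / 0.954 = 0.81 | 84% | 27 / 0.91 = 29.7 |
| 0.5 | 0.777 / 0.866 = 0.90 | 90% | 27 / 0.75 = 36.0 |
| 0.7 | 0.777 / 0.714 = 1.09 | 97.5% | 27 / 0.51 = 52.9 |

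With 30 per arm and d = 0.736 the powers are the same.

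**Dropout.** This was simulated with 39 per arm, two arms, baseline plus five visits, correlation 0.5 and a true difference of 0.777 SD. The first post-treatment visit was always observed. The chance of leaving followed a logistic function of the previous score, tuned to 30% lost by the last visit (5,000 runs per case). Entries are mean estimate / power at the last visit.

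| Log-odds slope on previous score | Completer t-test | Completer ANCOVA | Likelihood model, all visits |
|---|---|---|---|
| 0 | 0.771 / 79% | 0.774 / 89% | 0.774 / 89% |
| 0.3 | 0.775 / 80% | 0.779 / 89% | 0.782 / 90% |
| 0.7 | 0.723 / 76% | 0.747 / 86% | 0.774 / 88% |
| 1.2 | 0.675 / 70% | 0.724 / 85% | 0.780 / 90% |

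At the steepest slope the bias is 0.777 - 0.675 = 0.10 SD for the t-test and 0.777 - 0.724 = 0.05 SD for completer ANCOVA. Type I error at slopes 0 and 1.2 was 4.8% to 5.5% for all three methods.

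**Familywise error.** With three equal arms of 27 at one visit (200,000 runs), three uncorrected t-tests reject at least once in 12.2% of trials. A joint F-test at 0.05 followed by pairwise tests gives 5.0%, and 4.9% to 5.0% when one arm truly differs. Over five visits, the 15 uncorrected tests give about 23% to 45% for between-visit correlations of 0.9 down to 0.3 (8,000 runs per setting).

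**Cost of testing jointly first.** Power for the largest pairwise difference (0.777 SD, 27 per arm), with the middle arm either halfway or equal to the lowest arm:

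| r | Middle arm halfway | Middle arm equal to lowest |
|---|---|---|
| 0 | 70% | 76% |
| 0.3 | 74% | 80% |
| 0.5 | 83% | 88% |
| 0.7 | 95% | 97% |

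**The case against.** The strongest reply is that the quoted sentence may not describe the arm comparison at all. The stated purpose is a correlation between ultrasound findings and severity, and the diagnostic section splits severity into two groups, which a two-sample test would suit. That is fair. It makes the precision, bias and error figures conditional on applying the tests to the arms. It does not rescue the plan, because on that reading the comparison of quantitative outcomes between arms has no named method at all.

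Other points stand in part:

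- Chi-squared can compare three arms for a qualitative outcome such as prolapse, so the concern is confined to quantitative outcomes.
- The plan states a 5% level and does not promise familywise control, so 12% is a consequence of leaving the rule open, not a broken guarantee.
- Much of the loss is efficiency. The completer t-test kept its Type I error in the cases simulated, and its bias was negligible when dropout was unrelated or weakly related to score.
- The likelihood model did well in a simulation that satisfied its own missing-at-random assumption. Its advantage in power over completer ANCOVA was small.
- Testing jointly first costs power. At a correlation of 0.3 the package gives 74% to 80%, against 80% for a single unadjusted t-test.

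**Conclusion.** The concern holds. For quantitative outcomes no three-arm, baseline-adjusted or repeated-measures analysis of the randomised comparison is specified, and this is certain from the text. The size of the harm is less certain, since it rests on assumed correlations and dropout patterns for which the documents offer no figures.

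The precision loss is relative to what the same data could give. It is not a shortfall against the stated 80% power, because 117 already allows for dropout. Baseline adjustment is worth making on its own. The joint test brings control of error across the three arms within one outcome, at a cost in power that baseline adjustment may not fully repay when the correlation is below about 0.5. This should be changed before outcome data are analysed, but it does not invalidate the design.

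**What to change.** State the randomised comparison explicitly in the SAP:

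1. For each quantitative outcome, fit a linear mixed model for repeated measures over the five post-baseline visits. Include baseline value, arm, visit and arm-by-visit terms, with unstructured within-woman covariance.
2. Analyse women in their assigned arm, using everyone randomised with at least one post-baseline value. Alternatively, put baseline in the outcome vector with a common mean across arms so that all women contribute.
3. Name one of the five visits as primary before outcome data are seen.
4. At that visit test the three arms jointly at 0.05. Go on to the three pairwise differences, with confidence intervals, only if that test is significant.
5. Use an ordinal baseline-adjusted model for the Oxford grade. The SAP should also say how Sandvik categories and markedly skewed outcomes are handled.
6. Keep the t and Mann-Whitney tests as sensitivity checks, and add one sensitivity analysis that departs from missing-at-random.

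The cost is SAP wording and slightly more analysis work in the SPSS 29 already named, with no new data. The model relies on missing-at-random, and step 4 has the power cost tabulated above. It does not control error across the several primary outcomes, which needs its own rule.

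### The Spearman analysis of the stated purpose does not fix which bladder neck measure, questionnaire or visit decides, and each test is read at p<0.05 with no hierarchy

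*Combined protocol and SAP*

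**What the plan says.** The Objectives section gives the purpose as follows: "evaluate the correlation between urethral instability, assessed by ultrasound analysis of the bladder neck opening, and the severity of SUI, assessed by validated standard questionnaires". It names no single questionnaire.

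The assessments paragraph of the Study Protocol Plan lists three instruments ("ICIQ-SF, King's Health Questionnaire, and Sandvik Severity Index") and describes them jointly as covering severity and quality of life. On timing, after the pre-intervention assessment, it says: "These assessments will be repeated at the end of the intervention and at 15 days, 3 months, 6 months, and 12 months post-intervention". That makes six occasions.

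The first paragraph of the SAP contains the whole correlation plan: "The correlation between variables will be analyzed using Spearman's correlation". It closes with "Statistical significance will be assumed with p-values <0.05". It gives no pair, visit, order of testing, multiplicity adjustment or exploratory label.

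The later SAP paragraphs, on diagnostic capacity, are more specific. They take dichotomised Sandvik severity as the gold standard, evaluate "bladder neck opening at rest, during the Valsalva maneuver, the variation between the two", and derive a cutoff for the opening at rest. They name no visit, and they do not say whether these choices also govern the Spearman analysis. The unit differs too: the entry criterion is in degrees, while the SAP cutoff is to be expressed in mm.

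**The concern.** The purpose reads as one question, but the plan supplies several ways to answer it: three versions of the opening, up to three questionnaires, and more than one visit. Each resulting coefficient would be judged at 0.05 by itself. Whoever runs the analysis can take any significant pair as showing that urethral instability is related to SUI severity. If rest against Sandvik were not significant but variation against ICIQ-SF were, the two results would not contradict each other, yet the plan would not say which of them answers the objective.

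The Objectives present this relation as a route to diagnosing severity with low-cost imaging. A chance correlation picked from several would be a weak basis for that.

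**Working it through.** **Is there a figure to reproduce?** The documents state no error rate for the correlation objective. Their only computed figure is the sample size (117, with 80% power, 5% significance and 30% dropout). It is given without an effect size or endpoint, so it can be neither reproduced nor tied to a correlation.

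**Inputs from the documents**
- Opening measures: rest, Valsalva, variation = 3 (SAP, diagnostic paragraphs).
- Questionnaires: 3 (assessments paragraph).
- Sandvik classes: mild, moderate, severe, very severe = 4 (SAP, diagnostic paragraphs).
- Level: 0.05 per test (SAP, first paragraph).
- n = 117, or 117 × 0.70 = 81.9, about 82, after the planned dropout.

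**Assumptions, not in the documents**
- No true association in any pair.
- Two-sided tests.
- One total score per questionnaire, with all three counted as severity measures in the nine-pair case.
- Variation = Valsalva minus rest.
- Rest-Valsalva correlation 0.3-0.8; correlation among questionnaires 0.3-0.9.

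**Step 1: number of baseline tests.** Sandvik only: 3 × 1 = 3. All questionnaires: 3 × 3 = 9.

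**Step 2: reference values if the tests were independent.** The chance of at least one p<0.05 is 1 − 0.95^k.
- k = 3: 1 − 0.857 = 14.3%.
- k = 9: 1 − 0.630 = 37.0%.

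**Step 3: allow for the correlation between tests.** The tests share data, so the true rates are lower. Ultrasound and questionnaire values were simulated independently of each other, with Sandvik cut into four classes, and each pair was tested by Spearman at two-sided 0.05 (10,000 replicates per setting). Ranges are over rest-Valsalva correlations of 0.3, 0.5 and 0.8.

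| Correlation among questionnaires | Any of 9 pairs, n=117 | Any of 9 pairs, n=82 |
|---|---|---|
| 0.3 | 31% | 31-32% |
| 0.5 | 28-30% | 28-30% |
| 0.8 | 24% | 23-25% |
| 0.9 | 20-21% | 20-21% |

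One named pair gave about 5% throughout. Three opening measures against Sandvik alone gave 12-13%. Smaller runs of 4,000 replicates spread slightly wider, at 11-13%. Over all the runs made, the nine-pair figure lay at about 20-33%. Sample size makes almost no difference.

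**Step 4: detectable correlation under the two possible fixes** (n = 117, 80% power, Fisher z).
- One test at 0.05: tanh[(1.960 + 0.842)/√114] = tanh(0.262) = 0.26.
- Holm's strictest step, 0.05/3: tanh[(2.394 + 0.842)/√114] = tanh(0.303) = 0.29.
- Spearman's coefficient has a somewhat larger variance than this formula assumes. With variance 1.06/(n − 3) in place of 1/(n − 3), the results are 0.26 and 0.30. Ties in a four-class index could add a little more.

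**The case against.** The best defence is that the diagnostic part of the SAP is the worked-out analysis of the purpose. The Objectives go on to speak of diagnosing severity, and the SAP then names Sandvik, the three opening measures and rest for the cutoff. A reader might infer from the Spearman sentence that the plan names no measure or questionnaire at all; that goes too far. What stands against the defence is that nothing carries those choices over to the correlation. Even if Sandvik is carried over, three opening measures remain, and no visit is named in either place.

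Other stronger readings also fail:

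- **A spurious finding is to be expected in 20-33% of cases.** The documents do not say that all nine pairs will be tested. They also describe the questionnaires as covering severity and quality of life, whereas the purpose concerns severity only. The figure holds only if no pair is truly associated, and it depends on assumed correlations.
- **Six visits give 6 × 9 = 54 tests.** The assessments are repeated, but nothing says the correlations are. Testing later visits would raise the rate; the documents support no particular figure.
- **The plan breaks its own 5% level.** The SAP states a per-test threshold and claims no rate over a family of tests. The fault is a missing decision rule, not a contradiction.
- **The randomised comparison is undermined.** This objective is observational and does not bear on the comparison of arms.

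**Conclusion.** The concern holds in limited form. For the only purpose that the Objectives section spells out, the Spearman plan leaves open which measure, questionnaire and visit decide, and it lets each test be read at 0.05. With no true association, the baseline chance of at least one significant result is about 11-13% if Sandvik is taken as the only severity measure, and about 20-33% if all nine pairs are tested. Using two questionnaires would fall between these. The figures are conditional on the assumptions listed in the working. The conclusion that a decision rule is missing does not depend on them. The sponsor should correct this before analysis, but it does not invalidate the trial.

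**What to change.** In the SAP, name one confirmatory correlation for the stated purpose: Spearman between bladder neck opening at rest and the Sandvik index, at the baseline visit, in all randomised women, two-sided 5%. These are the measure and the reference that the SAP already uses for its cutoff, and baseline avoids both dropout and any effect of treatment on the correlation. State the unit of the opening, and reconcile the degrees in the entry criterion with the mm in the SAP; otherwise the named pair remains ambiguous.

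Report every other correlation (Valsalva, variation, ICIQ-SF, King's Health Questionnaire, later visits) as exploratory, with estimates and confidence intervals and no claim of significance. If all three opening measures are meant to be confirmatory, test them against Sandvik at baseline with Holm's procedure instead.

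The cost is wording only, with no extra participants or data. The drawback is that the remaining correlations cannot be claimed as confirmed. Under the Holm option, the correlation detectable with 80% power at n = 117 rises from about 0.26 to about 0.30 at the strictest step.
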